**Figure 6-1. Semen Collection Schema**

A standardized procedure for semen collection and analysis will be provided to sites in a separate manual. Semen will be assessed locally for all parameters (motility, concentration, count, and volume), except morphology, which will be assessed centrally.

## 6.12. Vital Signs

Vital signs will be measured at the time points indicated in the Study Procedures Table ([Appendix 2](#)).

Vital signs should be taken after the subject has been resting for 5 minutes (please refer to [Appendix 12](#) for details) and will include heart rate, respiratory rate, systolic blood pressure (SBP), diastolic blood pressure (DBP), and body temperature.

## 6.13. Physical Examination

A PE will be performed at the time points indicated in the Study Procedures Table ([Appendix 2](#)).

Any changes from Baseline will be recorded. Height will be measured at Screening only. Weight without shoes is measured at all visits.

A complete PE, as detailed in [Appendix 12](#), will be performed at Screening only. Symptom-directed physical exams should be performed at all other visits, as needed.

## 6.14. Pharmacokinetic Assessments

Blood samples for PK analysis will be collected at least 30 minutes post-study drug dosing at the Week 2 visit, anytime at the Week 4 visit, and prior to study drug dosing at the Week 13 and 26 (only for subjects on open-label filgotinib in the Extension Phase) visits. Subjects should be instructed not to take their study drug on these visit days (except for the Week 4 visit) and bring it with them to the clinic instead.

Subjects will be instructed when to take their dose during their scheduled visit at the study site.

Plasma concentrations of filgotinib and its metabolite, GS-829845, will be analyzed.

### **6.15. High Sensitivity Serum C-Reactive Protein**

The subject's serum CRP will be measured using a hsCRP test at the time points indicated in the study activities table ([Appendix 2](#)).

Post-Baseline CRP results will be blinded up to and including Week 13 to the investigator until database lock.

### **6.16. 66/68-Joint Count (PsA) and 28-Joint Count (RA) (used for DAPSA and CDAI)**

For subjects enrolled with PsA, the 66/68 joint count will be used to calculate the DAPSA score. For subjects enrolled with RA, the 28 joint count will be used to calculate the CDAI score.

Each of 66/28 joints will be evaluated for swelling (swollen joint count 66/28 joints [SJC66/SJC28]) and each of 68/28 joints will be evaluated for tenderness (tender joint count 68 /28 joints [TJC68/TJC28]) ([Appendix 3](#)) at time points described in the Study Procedures Table ([Appendix 2](#)).

The 68/28 tender joint count should be performed by scoring the presence or absence of tenderness as assessed by pressure and joint manipulation.

The 66/28 swollen joint count should be performed by scoring the presence or absence of synovial fluid and/or soft tissue swelling (but not bony overgrowth) as assessed by pressure and joint manipulation.

### **6.17. Physician Global Assessment of Disease Activity (PhGADA)**

Global assessment of the subject's disease activity will be performed by drawing a perpendicular line on the visual analogue scale (VAS), and measuring the distance between the "no disease activity" anchor and the mark on the 10-cm line in mm.

The PhGADA will be recorded at the time points indicated in the Study Procedures Table ([Appendix 2](#)) and is provided in [Appendix 4](#).

### **6.18. Patient Global Assessment of Disease Activity (PtGADA) (used for CDAI and DAPSA)**

For subjects with RA and PsA, the patient's global assessment of their arthritis disease activity will be recorded on a 0 to 100 mm VAS. A perpendicular line will be drawn on the VAS, and with a ruler, the distance between the beginning of the line and the mark on the 10-cm line in mm will be the score from 0-100. A score of 0 indicates "very well" and 100 indicates "very poor" to the question "Considering all the ways psoriatic arthritis affects you, please draw a

vertical mark ( | ) on the horizontal line below for how well you have been doing over the last week.

The PtGADA will be recorded at the time points indicated in the Study Procedures Table ([Appendix 2](#)) and is provided [Appendix 5](#).

#### **6.19. Patient's Global Assessment of Pain Intensity (PPAIN) (used for DAPSA)**

For subjects with PsA, the patient's assessment of pain is a set of 2 questions on pain on the numerical rating scale.

The Patient's Global Assessment of Pain Intensity as related to arthritis will be recorded at the time points indicated in the Study Procedures Table ([Appendix 2](#)) and is provided in [Appendix 6](#).

#### **6.20. BASDAI**

For subjects with AS or nrAxSpA, the patient-reported arthritis activity will be measured at Screening using BASDAI. This is a 6-item index (fatigue, spinal pain, peripheral arthritis, enthesitis, intensity and duration of morning stiffness) in which the items will be recorded on a 0 to 10 numerical rating scale. The total score will range from 0-10.

The BASDAI will be assessed at the time points indicated in the Study Procedures Table ([Appendix 2](#)) and is provided in [Appendix 7](#).

### **7. ADVERSE EVENTS AND TOXICITY MANAGEMENT**

#### **7.1. Definitions of Adverse Events, Adverse Reactions, and Serious Adverse Events**

##### **7.1.1. Adverse Events**

An AE is any untoward medical occurrence in a clinical study subject administered a medicinal product, which does not necessarily have a causal relationship with the treatment. An AE can therefore be any unfavorable and/or unintended sign, symptom, or disease temporally associated with the use of a medicinal product, whether or not considered related to the medicinal product. AEs may also include pre- or post-treatment complications that occur as a result of protocol specified procedures, lack of efficacy, overdose, drug abuse/misuse reports, or occupational exposure. Pre-existing events that increase in severity or change in nature during or as a consequence of participation in the clinical study will also be considered AEs.

An AE does not include the following:

- Medical or surgical procedures such as surgery, endoscopy, tooth extraction, and transfusion. The condition that led to the procedure may be an adverse event and must be reported.
- Pre-existing diseases, conditions, or laboratory abnormalities present or detected before the Screening visit that do not worsen

- Situations where an untoward medical occurrence has not occurred (e.g. hospitalization for elective surgery, social and/or convenience admissions)
- Overdose without clinical sequelae (see Section [7.7.1](#))
- Any medical condition or clinically significant laboratory abnormality with an onset date before the consent form is signed and not related to a protocol-associated procedure is not an AE. It is considered to be pre-existing and should be documented on the medical history CRF.

### **7.1.2. Serious Adverse Events**

A serious adverse event (SAE) is defined as an event that, at any dose, results in the following:

- Death
- Life-threatening (Note: The term “life-threatening” in the definition of “serious” refers to an event in which the subject was at risk of death at the time of the event; it does not refer to an event that hypothetically might have caused death if it were more severe.)
- In-patient hospitalization or prolongation of existing hospitalization
- Persistent or significant disability/incapacity
- A congenital anomaly/birth defect
- A medically important event or reaction: such events may not be immediately life-threatening or result in death or hospitalization but may jeopardize the subject or may require intervention to prevent one of the other outcomes constituting SAEs. Medical and scientific judgment must be exercised to determine whether such an event is a reportable under expedited reporting rules. Examples of medically important events include intensive treatment in an emergency room or at home for allergic bronchospasm; blood dyscrasias or convulsions that do not result in hospitalization; and development of drug dependency or drug abuse. For the avoidance of doubt, infections resulting from contaminated medicinal product will be considered a medically important event and subject to expedited reporting requirements.

## **7.2. Assessment of Adverse Events and Serious Adverse Events**

The investigator or qualified subinvestigator is responsible for assessing AEs and SAEs for causality and severity, and for final review and confirmation of accuracy of event information and assessments.

### **7.2.1. Assessment of Causality for Study Drugs and Procedures**

The investigator or qualified subinvestigator is responsible for assessing the relationship to IMP therapy using clinical judgment and the following considerations:

**No:** Evidence exists that the adverse event has an etiology other than the study drug. For SAEs, an alternative causality must be provided (eg, pre-existing condition, underlying disease, intercurrent illness, or concomitant medication).

**Yes:** There is reasonable possibility that the event may have been caused by the IMP.

It should be emphasized that ineffective treatment should not be considered as causally related in the context of adverse event reporting.

The relationship to study procedures (eg, invasive procedures such as venipuncture or biopsy) should be assessed using the following considerations:

**No:** Evidence exists that the adverse event has an etiology other than the study procedure.

**Yes:** The adverse event occurred as a result of protocol procedures, (eg, venipuncture).

### 7.2.2. Assessment of Severity

The severity of AEs will be graded using the modified Common Terminology Criteria for Adverse Events (CTCAE), Version 4.03. For each episode, the highest grade attained should be reported.

If a CTCAE criterion does not exist, the investigator should use the grade or adjectives: Grade 1 (mild), Grade 2 (moderate), Grade 3 (severe), Grade 4 (life-threatening) or Grade 5 (fatal) to describe the maximum intensity of the adverse event. For purposes of consistency with the CTCAE, these intensity grades are defined in [Table 7-1](#) and [Appendix 9](#).

**Table 7-1. Grading of Adverse Event Severity**

Grade	Adjective	Description
Grade 1	Mild	Asymptomatic or mild symptoms; clinical or diagnostic observations only; intervention not indicated
Grade 2	Moderate	Local or noninvasive intervention indicated; limiting age-appropriate instrumental ADL*
Grade 3	Severe	Severe or medically significant but not immediately life-threatening; hospitalization or prolongation of hospitalization indicated; disabling; limiting self-care ADL**
Grade 4	Life-threatening	Urgent intervention indicated
Grade 5	Death	Death-related AE

\* Activities of Daily Living (ADL) Instrumental ADL refer to opening preparing meals, shopping for groceries or clothes, using the telephone, managing money, etc.

\*\* Self-care ADL refer to bathing, dressing and undressing, feeding self, using the toilet, taking medications, and not bedridden.

### **7.3. Investigator Requirements and Instructions for Reporting Adverse Events and Serious Adverse Events to the Sponsor**

#### Requirements for collection prior to study drug initiation:

After informed consent, but prior to initiation of study drug, the following types of events should be reported on the case report form (CRF/eCRF): all SAEs and AEs related to protocol-mandated procedures. All SAE's should also be reported via the paper SAE forms.

#### Adverse Events

Following initiation of study drug, collect all AEs, regardless of cause or relationship, until the last study visit must be reported to the CRF/eCRF database as instructed.

All AEs should be followed up until resolution or until the adverse event is stable, if possible. The sponsor may request that certain AEs be followed beyond the protocol-defined follow-up period.

#### Serious Adverse Events

All SAEs, regardless of cause or relationship, that occurs after the subject first consents to participate in the study (ie, signing the informed consent) and throughout the duration of the study, including the protocol-required post-treatment follow-up period, must be reported to the CRF/eCRF database and the Sponsor as instructed. This also includes any SAEs resulting from protocol-associated procedures performed after informed consent is signed.

Any SAEs and deaths that occur during any portion of the study or after study discontinuation but within 30-days of the last dose of study IMP, regardless of causality, should also be reported.

Investigators are not obligated to actively seek SAEs after the protocol defined follow up period however, if the investigator learns of any SAEs that occur after study participation has concluded and the event is deemed relevant to the use of IMP, he/she should promptly document and report the event to the Sponsor.

All AEs and SAEs will be recorded in the CRF/eCRF database and all SAE's should also be reported via the paper SAE form within the timelines outlined in the CRF/eCRF completion guideline.

During the Monitoring Phase, all AEs related to the protocol-mandated procedures, and all SAEs (regardless of relatedness) should be reported on the case report form (CRF/eCRF).

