### 3.3. Monitoring Phase (up to 52 weeks)

Figure 3-4. Monitoring Phase - Evaluation

\*Adjustment of background treatment with non-prohibited medication allowed at any time during the Monitoring Phase

Subjects whose sperm parameters meet any of the pre-specified decrease thresholds will switch to the Monitoring Phase immediately. Subjects on double-blinded treatment or open-label filgotinib who enter the Monitoring Phase will discontinue study drug and start Standard of Care. These subjects will also have a safety follow-up visit 30 days after last study drug dose. Subjects on Standard of Care will continue treatment.

All subjects who enter the Monitoring Phase will undergo semen evaluations every 13 weeks starting from their entry into the Monitoring Phase, for up to 52 weeks or until Reversibility (see [Definition of Terms](#)) is met, whichever is achieved first.

In case a subject needs to be treated with a prohibited medication (see [Table 5-1](#)), for instance to control their rheumatic condition, the subject will discontinue the study and complete an ET visit (including semen collection).

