Assessment of Adverse Events	X	X	X	X	X	X	X	X
Semen Collection (2 samples as per collection instructions in Section 6.11) i	X					X	X j	
Date and time of most recent ejaculation k	X					X	X	
HIV, Hepatitis B, and Hepatitis C l	X							
HBV DNA l, m						X		
Randomization		X						

EVENT	Screening						ET b	Safety follow-up c 30 Days after last dose of study drug (±5 days)
		Day 1	W2 (±5 days)	W4 (±5 days)	W8 (±5 days)	W13** (+5 days)		
Study days (D)/weeks (W) a								
Study Drug Accountability				X	X	X	X	
Study Drug Dispensation a		X		X	X	X o		
In-clinic Dosing a		X	X			X		

a Visits correlate with the number of days/weeks on drug.

b Any time a subject discontinues participation in the study prior to Week 13 an Early Termination (ET) Visit is required. Subjects who are Responders at Week 13 and choose not to continue in the Extension Phase are also required to complete ET visit assessments.

c All subjects will have a 30-day safety follow-up visit after discontinuing blinded study drug, except Arthritis Responders at Week 13 who are continuing in the Extension Phase of the study.

c As detailed in [Appendix 12](#).

d For definitions of Arthritis Responder/Non-responder status please refer to [Definition of Terms](#).

e Proof of no active or untreated latent tuberculosis (TB) at Screening. Subjects who are diagnosed with latent TB at Screening must initiate an adequate course of prophylaxis as per local standard of care for a minimum of 4 weeks prior to randomization. Subject may initiate study drug dosing only after consultation with the Sponsor Medical Leader or designee.

f Chest x-ray (views as per local guidelines) taken at Screening or within the 3 months prior to Screening (with the report or films available for investigator review) without evidence of active or latent TB infection.

g As detailed in [Appendix 11](#). For visits that require fasting, subjects should not have any food or drink (except water) for at least 8 hours before the visit.

h Sparse plasma pharmacokinetic (PK) samples at Week 2 are collected at 30 minutes post dose. The PK sample at Week 4 can be collected at any time without regard to dosing. The PK sample at Week 13 is collected prior to study drug administration. Please refer to Section [6.14](#) for details on study drug administration.

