8.1.5. Treatment-Emergent Adverse Events

8.1.5.1. Definition of Treatment-Emergent Adverse Events

Treatment-emergent adverse events (TEAEs) during the double-blind phase are defined as 1 or both of the following:

- Any AEs with an onset date on or after the double-blind study drug start date through first dose date of open-label filgotinib/start date in extension phase minus 1 day (if subject enrolled in extension phase) or to last dose date of double-blind study drug + 30 days for subjects who permanently discontinue double-blind drug and do not enroll into extension phase (including subjects who meet a sperm decrease threshold who stop study drug and continue to be followed in the monitoring phase for reversibility)
- Any AEs leading to premature discontinuation of double-blind study drug

Treatment-emergent adverse events (TEAEs) during the extension phase are defined as 1 or both of the following:

- Any AEs with an onset date on or after first dose date of open-label filgotinib/first dose date in extension phase to last dose date of open-label filgotinib + 30 days for subjects who permanently discontinue open-label filgotinib (including subjects who meet a sperm decrease threshold who stop study drug and continue to be followed in the monitoring phase for reversibility) or all AEs for subjects who are ongoing on open-label filgotinib/standard of care in extension phase at the time of an interim analysis
- Any AEs leading to premature discontinuation of open-label filgotinib study drug

For example, for a subject who took double-blind placebo and switched to standard of care in the extension phase, TEAEs with an onset date on/after first dose date of double-blind filgotinib and prior to first date in extension phase will be TE for double-blind filgotinib (summarized with double-blind phase); from first date in extension phase up to last dose date of standard of care in extension phase + 30 days will be TE for standard of care (summarized by treatment sequence [double-blind filgotinib to standard of care] for the extension phase).

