8.1.5.3. Analysis of Exposure-Adjusted Incidence Rate

The Exposure-Adjusted Incidence Rate (EAIR) for a TEAE is defined as:

$$\text{Incidence rate per 100 patient years of exposure (PYE)} \\ = \frac{\text{Total number of subjects with an event}}{\text{Total PYE}} \times 100.$$

The total patient-years of exposure (PYE) to a treatment is the sum of the individual subject's PYE and is defined as:

For subjects with an event:

$$\text{PYE} = (\text{Event start date} - \text{first date in DB phase} + 1) / 365.25$$

For subjects with no event:

$$\text{PYE} = (\text{Calculation end date} - \text{first date in DB phase} + 1) / 365.25$$

where calculation end date for the double blind phase = the earliest date among

(last dosing date of double blind phase +30, first date in extension phase of the study -1 day, death date, cutoff date). If the last study drug dosing date is missing and the subject has stopped drug, the latest date among study drug end date, clinical visit date, and laboratory sample collection date that occurred during the double-blind phase will be used.

where calculation end date for the entire study display = the earliest date among

(last dosing date of OL filgotinib+ 30 days [subjects in the filgotinib to OL filgotinib sequence who permanently discontinued OL filgotinib]; last dosing date of double-blind filgotinib [subjects in the filgotinib to standard of care group], last date on standard of care in extension phase [subjects in placebo to standard of care sequence who switched to monitoring phase or early terminated from study after starting extension phase], last dosing date of double-blind study drug + 30 for subjects who did not start extension phase, data cutoff date, death date).

If event start date during the double-blind phase is partially missing and the non-missing portion matches the first dosing date (month and/or year) of double-blind study drug; or if the date is completely missing, AE onset is imputed as the date of first dose of double-blind study drug. Otherwise it is imputed as the first day of the month (if only day is missing) or January 1st of the year (if day and month are missing).

The exact 95% CI based on the Poisson distribution [{Ulm 1990}](#) for EAIR is defined as:

$$\left(\frac{\chi^2_{2(\text{Total number of subjects with an event}), 0.025}}{2 \times \text{Total PYE}}, \frac{\chi^2_{2(1+\text{Total number of subjects with an event}), 0.975}}{2 \times \text{Total PYE}} \right) \times 100.$$

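### Protocol 7.3 gives two conflicting AE collection rules, and the narrower one, read literally, leaves a gap in the 30-day treatment-emergent window that the SAP applies to men entering the Monitoring Phase

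*Protocol*

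**What the plan says.** Protocol 7.3 states two rules. Under its Adverse Events heading: "Following initiation of study drug, collect all AEs, regardless of cause or relationship, until the last study visit must be reported to the CRF/eCRF database". No exception is made for the Monitoring Phase. Under its Serious Adverse Events heading: "During the Monitoring Phase, all AEs related to the protocol-mandated procedures, and all SAEs (regardless of relatedness) should be reported". The AE row of the Monitoring Phase table in Protocol Appendix 2 carries a footnote that only refers back to Section 7.3.

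On timing, Protocol 3.3 says that men meeting a threshold "will switch to the Monitoring Phase immediately" and that those on double-blind drug or open-label filgotinib stop it. It adds: "These subjects will also have a safety follow-up visit 30 days after last study drug dose".

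On analysis, Protocol 8.5.6 treats AEs as treatment-emergent up to 30 days after permanent discontinuation. SAP 8.1.5.1 uses last dose plus 30 days for men who stop double-blind drug and do not enter the Extension Phase, "including subjects who meet a sperm decrease threshold who stop study drug and continue to be followed in the monitoring phase for reversibility". SAP 8.1.5.3 ends double-blind person-time at the earliest of several dates, one of them "last dosing date of double blind phase +30".

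**The concern.** The analysis window and the collection rule should cover the same days. Under the narrower rule they do not. A non-serious infection or herpes zoster on day 15 after the last dose would be treatment-emergent, and SAP 8.1.7 lists both as adverse events of interest (AEIs). Yet a site following the Monitoring Phase sentence need not record it, while the man's follow-up still enters the denominator. Two sites could follow different sentences of the same section and both comply.

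The affected men are those selected by the trial's main safety outcome, a sperm decrease of at least 50%. If more of them come from one arm, any under-recording would fall more heavily on that arm.

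**Working it through.** The plan states no figure on this point, so there is none to reproduce. The check compares the two windows and then sizes the worst case.

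**Comparison for a man who meets a threshold at Week 13**

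| Item | Source | Coverage of the 30 days after last dose |
|---|---|---|
| General AE rule | Protocol 7.3, Adverse Events | All AEs |
| Monitoring Phase rule | Protocol 7.3, Serious Adverse Events | Procedure-related AEs and all SAEs |
| Day-30 safety visit | Protocol 3.3, Appendix 2 | AE assessment marked |
| TEAE window | Protocol 8.5.6, SAP 8.1.5.1 | Included |
| Double-blind person-time | SAP 8.1.5.3 | Included |

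The Monitoring Phase sentence reads most naturally as a restriction. Section 7.3 uses nearly the same formula for the period between consent and first dose, where it plainly limits collection. If the general rule applied throughout, the sentence would add nothing.

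**Inputs**
- D = 91 days on double-blind drug (13 weeks, Protocol 3.6). As a variant, D = 112, the upper limit of the Week 13 semen window in SAP Table 3-4.
- 30 days after last dose (SAP 8.1.5.1 and 8.1.5.3).
- f = fraction of an arm entering Monitoring at Week 13. The documents give no rate; 5% to 15% is assumed.
- Men entering the Extension Phase get no added 30 days, because their double-blind time ends the day before it starts.

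**Per affected man**, uncovered share = 30/(D + 30):
- D = 91: 30/121 = 24.8%
- D = 112: 30/142 = 21.1%

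**Per arm**, uncovered share = 30f/(91 + 30f):
- f = 5%: 1.5/92.5 = 1.6%
- f = 10%: 3.0/94.0 = 3.2%
- f = 15%: 4.5/95.5 = 4.7%

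With a constant event rate and no capture at all in the 30 days, these are also the proportions by which an arm's rate of non-serious, non-procedural events would be understated.

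**Between arms**, the rate ratio (filgotinib/placebo) is multiplied by [91/(91 + 30f₁)] / [91/(91 + 30f₂)] = (91 + 30f₂)/(91 + 30f₁), where f₁ is the filgotinib fraction and f₂ the placebo fraction:
- equal fractions: 1.000
- 10% vs 5%: 92.5/94.0 = 0.984
- 15% vs 5%: 92.5/95.5 = 0.969
- 5% vs 10%: 94.0/92.5 = 1.016

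With full capture at the day-30 visit, every factor is 1.

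**Which outputs are exposed.** SAP 8.1.7 applies exposure-adjusted rates only to AEIs and SAEs. SAEs are collected under both rules, so only non-serious AEIs can move those rates. Plain TEAE counts and percentages are exposed for every non-serious, non-procedural AE, although a man already counted for an earlier event in the same category is not lost, since SAP 8.1.6 counts each subject once per summary.

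**Entire-study display.** SAP 8.1.5.3 adds 30 days for men who stop open-label filgotinib, but ends time at the last standard-of-care date for placebo-to-standard-of-care men who enter Monitoring. Any under-recording after the Extension Phase would therefore touch the filgotinib rate only.

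**The case against.** A reader might infer that non-serious AEs are simply not collected in the Monitoring Phase. The documents do not support that. The general rule says AEs must be reported to the last study visit, while the narrower sentence says only what should be reported. The paragraph just before the narrower sentence states that all AEs and SAEs go into the CRF/eCRF database. Procedure-related non-serious AEs are collected even on the narrow reading. No text says that the narrower sentence governs the CRF, and the completion guideline to which 7.3 refers is not among the documents.

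The 30-day window also has its own visit for these men. Appendix 2 says: "All subjects will have a 30-day safety follow-up visit after discontinuing blinded study drug, except Arthritis Responders at Week 13". AE assessment is marked at that visit in both the double-blind and Extension Phase tables, with no restricting footnote. One coherent reading is that full AE assessment covers the 30 days and the narrow rule starts with the later 13-weekly Monitoring visits.

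All of this stands, and it suggests that full capture was probably intended. It does not remove the contradiction. Nothing says that the safety visit overrides the Monitoring Phase sentence, so a site could assess an AE at day 30 and, on that sentence, conclude that it need not be recorded.

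**Conclusion.** The contradiction within Section 7.3 is real. Its effect on the safety tables is a risk whose realisation depends on which rule the sites and the eCRF guideline followed. The uncovered share lies between zero (full capture at day 30) and 24.8% of the double-blind window per affected man. At arm level the worst case is 1.6% to 4.7%, given 91 days on drug, a constant event rate, no capture in the window and an assumed 5% to 15% entering Monitoring at Week 13. That is small overall, but concentrated in the men of most interest.

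Two stronger conclusions are tempting and not supported. One is that AEs have been under-counted: the documents show only that the instructions permit it. The other is that the comparison favours filgotinib: in the double-blind phase both arms are affected alike unless Monitoring entry differs by arm, and the documents give no entry rates. Even 15% against 5% with no capture moves the rate ratio only to 0.969 of its true value.

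**What to change.** Reconcile the two sentences of Protocol 7.3: all AEs are recorded up to 30 days after the last study drug dose, whatever the phase, and the narrower rule applies only to later Monitoring Phase time. This brings collection into line with Protocol 8.5.6 and SAP 8.1.5.1 and 8.1.5.3. It costs one sentence and a matching line in the eCRF guideline; the day-30 visit with AE assessment already exists.

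The change cannot recover past data. The Amendment 2 rationale says the study is already beyond the time points of its primary, secondary and exploratory endpoints, so new wording helps only men who enter Monitoring later, from the Extension Phase. For men already past the window, confirm which rule the eCRF guideline applied. If it was the narrower one, disclose this in the clinical study report, where SAP Section 1 places changes made after finalization. Also add a sensitivity analysis that ends TEAE and exposure time at Monitoring Phase entry. That needs one rerun of the affected tables and no new data.
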